# 6 Study design and setting

# Phase 1a (Intervention Adaptation)

We will establish an Intervention Adaptation Group (IAG) comprised of 6 to 8 key stakeholders who will be representatives from our PPI partners, carers and family members, people with autism and/or intellectual disabilities, and clinicians, along with members of the research team. The IAG will comprise of 6-8 key stakeholders who will be representatives from our PPI partner, parents/carers, young people with LD, and therapists, along with members of the research team.

This group will work collaboratively over a series of 5 meetings over 5 months to:

(a) define the needs and problems that are to be addressed for children and adolescents with moderate–severe LD and specific phobia

- (b) define the intervention objectives, with reference to likely barriers
- (c) adapt the existing manualised treatment
- (d) develop a logic model

(e) develop a fidelity checklist, based on approaches that have been successful in our recent

- LD trials within UK NHS settings (34)
- (f) advise on recruitment pathways
- (g) establish how to measure outcomes
- (h) consider the challenges / barriers to our evaluation plan, including likely solutions

Feedback will be sought at each meeting, and following reflection, subsequent refinements will be made to the manual and fidelity checklist by the research team, to then be presented to the IAG at the next meeting. This will include a series of candidate outcome measures. The IAG will be invited to make a final recommendation as to which outcome measures should be used within Phase 2 of the study. A broad range of potential measures will be considered, including parent/carer questionnaires, behavioural measures, and physiological measures (e.g. heart rate).

We will use co-applicant [name]' existing intervention (10, 29) that was developed for dog phobia in adolescents with severe LD and little to no speech. Importantly, this intervention was developed explicitly for children with severe LD and limited communication skills, and evaluated in that population (10, 29).

We will adapt this intervention to be developmentally appropriate for use with both children and adolescents, with moderate–severe LD, and with phobia related to any specific stimulus, as defined by the DSM-5 (Animal, Natural Environment, Blood-injection-injury, Situational, Other). The adaptation will include facilitation/support for communication impairments. This is likely to include the introduction of rich and multiple media to support and facilitate understanding. This will require the selection of meaningful vocabulary, specifically the development of a tailored lexicon to support treatment with augmentation of meanings through multiple media, e.g. photo symbols, line drawings, manual sign and gesture.

We will also adapt the delivery of the intervention to be parent-mediated, with therapist support and initial training. We anticipate that the adapted intervention will consist of two parts: (i) a parent/carer skills training group workshop (over 1 day), and (ii) weekly therapist support telephone calls with individual parents.

The outcomes from Phase 1a will be: (a) an adapted intervention manual that can be tested within a feasibility study (Phase 2), (b) a fidelity checklist, and (c) candidate outcome measures for use within the Phase 2 feasibility study.

# Phase 1b (TAU Survey)

Design: Using an online survey (UK wide) of parents who identify their child (aged 5-15 years) with moderate—severe LD as having a specific phobia (minimum n=50), together with interviews / online survey of professionals, this phase of the project will determine current community-based treatment as usual (TAU).

Questions for the parent survey will include the type of support/treatment, who, how and where it is delivered, along with dose and any modifications. The online survey will be delivered using Qualtrics. There will be one survey response per household.

We will also conduct a series of telephone interviews with LD health professionals, service providers, and commissioners (N=25), covering the same content as the parent survey. Interviews will also be offered in a form of an online survey. Professionals will be recruited via the Child and Adolescent Intellectual Disability Psychiatry Network in the UK (co-applicant [name] is secretary) and similar clinical psychology networks of which co-applicant [name] is a member. We will also work with the Research in Developmental Neuropsychiatry (RADIANT) consortium of NHS providers to recruit professionals for the interviews/survey. The sampling strategy is based on an estimate of the number of interviews/survey responses (N= 25) needed to achieve thematic saturation (44).

Reading CAL East Anglia

Analysis of the survey and interview data will use a framework adapted from the Template for Intervention Description and Replication (TIDieR) checklist (45) to characterise TAU from the perspective of parents and professionals. The TIDieR checklist is used to provide a description of an intervention, including associated materials, by whom, how, and where an intervention is delivered is described, as well as the dose, and any modifications. The interview data will be managed and analysed using NVivo (University Warwick site licence).

Setting: We will utilise our existing Midlands and wider UK networks of schools, support groups, charities, our PPI partner (the Foundation for People with Learning Disabilities) to disseminate the online survey to parents of children and adolescents throughout England, Wales, Northern Ireland, and Scotland. We will also use our existing LD health professional networks, together with the local NIHR Clinical Research Network.

# Phase 2 (Feasibility Study)

Co-applicant [name] has developed an exposure-based intervention for children with severe LD and limited communication skills, and through a series of cases studies, has demonstrated successful treatment delivery and outcomes. This intervention, which is already designed to accommodate the necessary augmented communication strategies, as well as dealing with behavioural, repetitive, and sensory difficulties often experienced by this population, will form the basis of the intervention adapted in Phase 1.

Using the intervention developed within Phase 1 of the current study, we will complete a feasibility study to model the intervention and determine its acceptability and feasibility for stakeholders, including service users, parents/carers, and clinicians, as per the Medical Research Council (MRC) Framework for the development of complex interventions (53).

Design: A single arm, non-randomised, feasibility study, with participants who will receive the adapted intervention developed in Phase 1a. We propose to recruit 20 participants and their parental caregivers (N=20), who will receive the intervention, in conjunction with any other treatment they are currently receiving. Children currently receiving treatment for specific phobia or psychological intervention for other anxiety disorders will not be eligible to participate.

Participants will be assessed at three times points: (1) screening, (2) baseline assessment within 4weeks before commencement of the intervention, and (3) assessment at completion of the intervention. Additional components of feasibility (e.g. acceptability) will be assessed using semistructured interviews and qualitative analysis, described below.

Setting, Context, and Trial Pathway: This single arm non-randomised feasibility study will take place within the NHS - either specialist LD or mainstream child and adolescent mental health services in England. We will use a multi-point recruitment strategy, including NHS services, special schools, and parent support groups, together with NIHR Clinical Research Networks. In addition, we will work with the Research in Developmental Neuropsychiatry (RADiANT) consortium of NHS providers to maximise recruitment. RADiANT is a consortium of NHS service providers which works in collaboration with academics in a number of universities. It seeks advice from service users, patients, families, charities, community leaders and a range of statutory bodies and organisations. RADiANT focuses on mental health and behavioural issues associated with five developmental conditions, including Learning Disability (LD) and Autism Spectrum Disorders (ASD). The consortium is co-convened by [name], Associate Dean, Royal College of Psychiatrists and [name], University of Warwick (and co-applicant on this proposal). The Coventry and Warwickshire Partnership NHS Trust and the Herefordshire Worcestershire Health and Care NHS Trust Learning Disabilities service have agreed to be a recruitment site. Using these existing networks will facilitate the timely recruitment of participants into the study.

The steps in the pathway for the feasibility study are as follows:

- a) all participants who consent to participate in the study will be screened by research staff to ensure they meet the inclusion criteria for the study (parent/guardian consent, child assent),
- b) following baseline assessment, participants who meet eligibility criteria will receive the intervention (plus treatment as usual),
- c) participants will be assessed using the study outcome measures within 4 weeks of completion of the intervention,
- d) a subsample of participants (parents/carers) and the therapists will be invited to take part in semi-structured interviews following completion of the intervention to further assess acceptability, their experience of the intervention, the study pathway, procedures, consent, and associated factors in order to provide a description of the factors that facilitate or challenge the implementation of the intervention,
- e) a subsample of young people (up to 5, predominantly with moderate LD) who received the intervention will be interviewed to explore their experience of the treatment and their outcomes, and
- f) through the Study Steering Committee, make a recommendation to the funders for their consideration as to whether a future clinical trial is feasible.

### 6.1 Risk assessment

A Study Risk Assessment has been completed to identify the potential hazards associated with the study and to assess the likelihood of those hazards occurring and resulting in harm. This risk assessment includes:

- The known and potential risks and benefits to human participants
- How high the risk is compared to normal standard practice
- How the risk will be minimised/managed

This study has been categorised as low risk, where the level of risk is comparable to standard care. A copy of the study risk assessment may be requested from the Study Manager. The study risk assessment is used to determine the intensity and focus of monitoring activity (see Section 25.1).

# 7 Site and investigator selection

This study will be carried out at participating sites within the United Kingdom. All sites who are interested in participating in the study will be required to confirm capability and capacity to host the study to ensure they have adequate resources and experience to conduct the study.

Before any Site can begin recruitment a Principal Investigator at each site must be identified. The following documents must be in place and copies sent to the [contact] study email account (see contact details on page 4):

- Confirmation of capacity and capability in line with the information provided in the initial assessment letter and/or HRA approval letter.
- Authorised Organisational Information Document (Non-Commercial) with completed local details.
- Current Curriculum Vitae and GCP training certificate of the Principal Investigator (PI)
- Completed Site Delegation Log and Roles and Responsibilities document
- Full contact details for all host care organisation personnel involved, indicating preferred contact

Reading CAL East Anglia

• A copy of the most recent approved version of the Participant Information Sheet(s) and Consent Form(s) on host care organisation headed paper

Upon receipt of all the above documents, the Study Manager will send written confirmation to the Principal Investigator/lead Research Nurse detailing that the centre is now ready to recruit participants into the study. This letter/email must be filed in each site's Site File. Along with the written confirmation, the site should receive all the documents required to recruit into the study.

Occasionally during the study, amendments may be made to the study documentation listed above. The study team will issue the site with the latest version of the documents as soon as they become available. It is the responsibility of the study team to ensure that new documents have the associated correct approvals.

Site initiation will be by tele- or videoconference if attendance of key personnel in person is unfeasible.

# 8 Participant selection

Participants are eligible for Phase 2 of the study if they meet all the following inclusion criteria and none of the exclusion criteria apply. All queries about participant eligibility should be directed to the Study Manager.

# 8.1 Inclusion criteria

- aged 5-15 years
- existing diagnosis of moderate to severe LD, confirmed at screening
- suspected / diagnosed specific phobia (DSM-5), confirmed at screening
- parent/carer able to participate in the intervention.

# 8.2 Exclusion criteria

- currently receiving another psychological therapy for anxiety
- screening indicates anxiety behaviours are likely associated with a physical health condition (e.g. dental problems)
- no consent obtained to take part in the research

# 9 Recruitment, screening, and registration

#### 9.1 Participant identification

We will use a multi-point recruitment strategy, including NHS services, special schools, and parent support groups, together with the local NIHR Clinical Research Network. In addition, we will work with the Research in Developmental Neuropsychiatry (RADIANT) consortium of NHS providers to maximise recruitment. The Coventry and Warwickshire Partnership NHS Trust and the Herefordshire Worcestershire Health and Care NHS Trust Learning Disabilities service are also recruitment sites. Information about the study will be placed within the public domain upon our website and the Foundation for People with Learning Disabilities website.

Where eligible participants need to be identified prior to consent being taken, screening will be conducted by clinicians who routine access to personally identifiable information (e.g. nursing staff working within a community teams for people with learning disabilities). This initial screening will take place only within the NHS and may involve a search of patient records or discussion with clinician teams. The personally identifiable information required for screening is diagnosis which will be taken from clinical records, specifically a diagnosis of moderate to severe learning disabilities and information to suggest that the person has problems with specific phobia and whether they are already receiving psychological therapy. This will be checked by a clinician outside of the study team who will then share information about the study with participants and/or carers. Screening will also include parent / carer completion of the domain level version (over the telephone or in person) of the Vineland Adaptive Behaviour Scales 3 (57) which will index severity of intellectual disability and confirm they have a moderate-severe LD with reference to the VABS Composite score (a standard score below 55), and confirmation of a diagnosis of Specific Phobia using an LD-sensitive diagnostic manual checklist based on the Diagnostic Manual - Intellectual Disability-2. The site PI will confirm eligibility with the CI.

Clinicians will then share information about Phase 2 of this study with likely eligible participants and/or carers. Participants and/or carers will then have contact with the study team via two possible routes:

(a) Participants (parents) tell clinicians that they want their contact details passed to the study team when asked. The study team will receive the details from clinicians and then contact the participants and/or carers. (b) Participants (parents) contact the study team directly using the contact information they were provided.

**Evelina**London

There is a third route which is for those participants who are identified via schools, voluntary, charitable sectors, or for those who self-refer:

(c) Participants (parents) will have contacted the study team directly using contact information they would have seen on websites or within adverts (e.g. information within newsletters or emails sent to parents via their child's school).

Potential participants will be contacted by Research Assistants from the study team to arrange a short screening/recruitment interview, either by telephone or face-to-face. During the screening/recruitment telephone interview the following will be carried out:

- The study will be explained in detail, including the randomisation and consent process and participants will be sent/left with a copy of the information sheet to consider.
- Screening consent (either written if face-to-face or verbal if over the telephone) will be obtained to complete the screening measures only.

Screening measures will be taken to establish eligibility. Screening will include parent / carer completion of the domain level version (over the telephone or in person) of the Vineland Adaptive Behaviour Scales 3 (57) which will index severity of intellectual disability and confirm they have a moderate-severe LD with reference to the VABS Composite score (a standard score below 55), and confirmation of a diagnosis of Specific Phobia using an LD-sensitive diagnostic manual checklist based on the Diagnostic Manual - Intellectual Disability-2.

 Following the screening visit, the research assistant or Study Manager will confirm eligibility with the CI. If eligible, the Research Assistant will arrange a recruitment/baseline visit. If any concerns are raised during the screening visit (i.e the family are in crisis), the PI will signpost the family to appropriate local support. Working guidelines for this will be established.

The research team will take responsibility for definitive screening to determine eligibility.

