# 1 Amendment History

The following amendments and/or administrative changes have been made to this protocol since the implementation of the first approved version.

Version approved by the ethics committee was 3.0.

Amendment No.	Protocol version no.	Date issued	Summary of changes made since previous version
1	3.1	28.07.2021	- We have added an option to offer the telephone interviews with professionals as an online survey. The questions remain the same.

shire and Worce

Coventry and ershire Warwickshire Partnership

#### Synopsis 2

Short title	Treating specific phobias		
Acronym	SPIRIT		
Internal ref. no.	Ideate: 64325		
Development phase	Feasibility		
Funder and ref.	National Institute for Health Research - Ref: NIHR130177		
Study design	Phase 1a: intervention adaptation. Phase 1b: online survey and interviews to describe treatment as usual (TAU). Phase 2: single-arm feasibility study		
Study participants	
 
Phase 1a: Intervention Adaptation Group (IAG) will be comprised of 6-8 key stakeholders who will be representatives from our PPI partners, carers and family members, young people with learning disabilities, and clinicians, along with members of the research team.
 
Phase 1b: parents who identify their child with moderate–severe learning disability as having a specific phobia, learning disability professionals (health professionals, service providers, and commissioners)
 
Phase 2: Children and adolescents aged 5-15 years, with a diagnosis of moderate–severe learning disability who have a suspected specific phobia (confirmed at screening), together with their parental caregiver(s).
 
		
Planned sample size	Phase 1a: 6 to 8. Phase 1b: minimum of 50 parents, 25 learning disability professionals. Phase 2: 20 participants and their parental caregivers (20)		
Planned number of sites	Phase 1b: up to 20 sites for survey of TAU Phase2: 2 sites for recruitment of participants for intervention modelling		
Inclusion criteria	
 
Phase 1b: parents who identify their child with moderate–severe learning disability as having a specific phobia.
 
Phase 2: (a) diagnosis of moderate–severe LD confirmed at screening, (b) diagnosis (DSM-5) of specific phobia, confirmed at screening, (c) parent/carer able to participate in the intervention.
 
		

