#### Phase 2: Feasibility Study

Our objectives are to:

- (i) evaluate the manualised intervention to determine the acceptability and feasibility for all stakeholders, including children and young people, carers, and therapists,
- (ii) judge the appropriateness of our measures of anxiety-related symptomatology, and secondary outcomes, for use within a larger study,
- (iii) explore recruitment pathways,
- (iv) determine the feasibility and acceptability of consent and associated processes,
- (v) describe factors that facilitate or challenge the implementation of our intervention
   (e.g. comorbid behaviour problems, other mental health problems, community
   resources to support exposure),
- (vi) determine acceptability of randomisation in a future trial
- (vii) describe the parameters of a future study to examine effectiveness of exposure-based therapy to treat phobias in this population.

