# Reading L Viversity of Excelina London Hearing disabilities Excelina London Hearing disabilities Children's Healthcare

for the interviews/survey. The sampling strategy is based on an estimate of the number of interviews/survey responses (N= 25) needed to achieve thematic saturation (44).

The online survey and interviews will include questions that are informed by the Template for Intervention Description and Replication (TIDieR) checklist. The TIDieR checklist is used to provide a description of an intervention, including the use of any associated materials. Who, how and where an intervention is delivered is also described as well as the associated dose and modifications Example questions include, "Please provide the name or phrase that describes the intervention offered", "What are the key elements that are essential to the intervention?", "What materials are used in the intervention, including those given to participants or used in the delivery or training in the intervention?", "Who provides the intervention?". Our participant information sheets and consent forms for Phase 1b will be presented as part of our survey / interview. Respondents are expected to provide information on a single occasion.

**Phase 2**: Participants are expected to be enrolled in the study for approximately 6 months. Participants will be assessed at three times points: (1) screening, (2) baseline assessment within 4weeks before commencement of the intervention, and (3) assessment at completion of the intervention. Participants who meet eligibility criteria will be assigned to receive the intervention plus TAU, and we aim to provide the treatment within existing services within our sites.

The steps in the pathway for the feasibility study are as follows:

- a) all participants who consent to participate in the study will be screened by research staff to ensure they meet the inclusion criteria for the study (parent/guardian consent, child assent),
- b) following baseline assessment, participants who meet eligibility criteria will receive the intervention (plus treatment as usual),
- c) participants will be assessed using the study outcome measures within 4 weeks of completion of the intervention,

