## 12.2 Follow-up

There is only a single follow-up period for this study which is within 4-weeks of the completion of the intervention. For participants who discontinue treatment, and wish to remain enrolled in the study, data will be captured as per protocol. This means that data will be captured within the 4-week period following when treatment would have been completed had the participant continued to take part in the intervention.

Semi-Structured Interviews. We will examine the views of parents/carers and therapists to address key questions. Interviews will address: (a) intervention accessibility and acceptability, (b) helpful / unhelpful aspects, including barriers to change, (c) the value of our adaptations, (d) relationships with therapists within intervention, (e) acceptability of consent processes, (f) acceptability of outcome measures, and (g) acceptability of randomisation within a future trial. We will complete semi-structured interviews with up to 10 parents/carers and up to 10 therapists.

We will also complete interviews with up to 5 young people who received the intervention to explore their experience of the intervention and the outcomes for them. We recognise that interviewing participants with moderate-severe LD may be difficult due to associated communication difficulties and, for some participants with severe LD, they may not be able to take part within an interview process. We will make use of augmented communication methods to aid our interview as much as possible, such as Talking Mats which is a structured approach to helping people with communication difficulties to organise and express their views; these methods have been used previously with this population (60). For those who are not able to take part in Talking Mats-based interviews, we will rely on interviews with parents/carers.

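### Section 9.1 has staff explain randomisation to families at the screening interview, although Phase 2 is single-arm and non-randomised

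*Protocol*

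**What the plan says.** Section 9.1 of the Protocol lists what is done when a research assistant holds the screening/recruitment interview with a potential Phase 2 family. The first item reads: "The study will be explained in detail, including the randomisation and consent process". The family also receives the information sheet, and consent is taken for the screening measures.

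The design is described differently everywhere else:

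- Synopsis: "Phase 2: single-arm feasibility study".
- Section 6, Phase 2, Design: "A single arm, non-randomised, feasibility study, with participants who will receive the adapted intervention developed in Phase 1a".
- Section 6, Phase 2, Setting: "This single arm non-randomised feasibility study will take place within the NHS".
- Section 12, Phase 2: "Participants who meet eligibility criteria will be assigned to receive the intervention plus TAU".

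Randomisation does have a place in the study, but only as a question about later research. Objective (vi) in section 5.1 is to "determine acceptability of randomisation in a future trial", and interview topic (g) in section 12.2 is "acceptability of randomisation within a future trial".

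**The concern.** The section 9.1 bullet is an instruction for recruitment, not background. All three contact routes in that section lead to this interview: details passed on by a clinician, the family contacting the team with information from a clinician, and self-referral. The wording therefore applies to every family that reaches the interview. A parent who hears that the study involves randomisation may reasonably conclude that their child might not receive the intervention.

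This matters because of what the study measures. Section 5.2 names recruitment, reach, and the feasibility and acceptability of consent among the primary feasibility outcomes. Section 14.7 makes accrual a progression criterion and, under protocol adherence, also the acceptability of the consent procedures. A misdescription at first contact bears on each of these.

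**Working it through.** No figure is involved, so the check is a comparison of texts.

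**1. Can the wording refer to a future trial?** The synopsis objectives, section 5.1 (vi), section 12.2 (g) and section 15.1 all tie randomisation to a future trial, and the source data table in section 16 ties it to a larger trial. Section 9.1 has no such qualifier. It presents randomisation, with consent, as part of the study being explained. The future-trial reading does not fit.

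**2. Is there any allocation step in Phase 2?** The four descriptions of the design and of assignment quoted above agree with each other. Step (b) of the pathway, given in both section 6 and section 12, has all eligible participants go from baseline assessment to the intervention plus TAU. The text shows no allocation procedure, ratio or comparison arm. Section 9.1 stands alone.

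**3. Would a later, correct consent discussion repair it?** The protocol does not settle the order of events:

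| Place | What it implies |
|---|---|
| Section 9.1 | Consent at this interview covers the screening measures only |
| Section 9.4, Phase 2 | Screening data are collected only after consent to participate |
| Sections 6 and 12, step (a) | Those who have consented to the study are then screened |
| Figure 2 (schedule) | Informed consent is marked at screening and at no later time point |

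The last three rows put study consent at or before screening, so the explanation in section 9.1 may be the one on which it rests. If the first row governs instead, a family that declines at this interview never reaches the later discussion.

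**4. Who informs objective (vi)?** Section 12.2 says: "We will complete semi-structured interviews with up to 10 parents/carers and up to 10 therapists". According to section 6, step (d), the parents are a subsample of participants, interviewed after the intervention. A family put off at screening by the mention of randomisation cannot be among them. Any such loss would tend to remove the parents least willing to accept randomisation.

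**5. Size.** The protocol gives no refusal rate, with or without mention of randomisation, so the effect on accrual cannot be calculated.

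**The case against.** The strongest reply is that this is one stray phrase, probably carried over from another document, in a protocol that otherwise states its design consistently. Staff have no allocation procedure to describe. The Phase 2 consent text in section 9.4 has the information sheet and consent form sent in advance and does not mention randomisation. Views on future randomisation are already a separate interview topic. All of this is correct. It makes the point an inconsistency of wording and not a fault of design, but it does not make the bullet right.

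Three stronger readings are tempting, and the documents do not support them.

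- A reader might infer that consent in this study is misinformed. That is not shown. The information sheet, consent form and any interview script are not available, section 9.4 is silent on randomisation, and section 9.1 limits consent at this interview to screening. The unsettled order of consent leaves the risk open but does not establish it.
- A reader might infer that the interview answers on randomisation are contaminated because parents think they were randomised. By then they have been through a one-arm study in which every eligible family is assigned the intervention, and the topic is expressly about a future trial. The risk that remains is selection of who reaches the interview.
- A reader might put a number on lost accrual by assuming a refusal percentage. Any such percentage would come from outside the documents, and the result would only restate the assumption.

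**Conclusion.** The point holds as an internal inconsistency: section 9.1 refers to randomisation within a study that the rest of the protocol defines as single-arm and non-randomised. The contradiction itself rests on no assumption. The consequences are conditional on the bullet being followed as written. In that case it could misinform families at recruitment and deter some of them, which could bias recruitment, reach and consent acceptability, and would leave the deterred families out of the interviews on future randomisation. Neither the occurrence nor the size of these effects can be established from the protocol. The correction should still be made, because the error sits in a recruitment instruction and is simple to remove.

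**What to change.** In the section 9.1 bullet, delete the three words that refer to randomisation, so that the sentence covers the explanation of the study and the consent process only. Add a short statement that Phase 2 involves no randomisation and that all eligible families are offered the intervention. Keep randomisation solely as the hypothetical future-trial topic in section 12.2 (g). Check the information sheet, consent form and recruitment scripts for the same wording, and correct any that carry it.

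The cost is a one-line protocol correction and a read-through of the participant-facing documents. Design, sample size and analysis are unchanged.
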